### APPENDIX SECTION:

APPENDIX A INFORMED CONSENT

APPENDIX B ELIGIBILITY CHECKLIST

APPENDIX C ADVERSE DRUG REACTION MEMORANDUM

APPENDIX D COMMON TOXICITY CRITERIA

APPENDIX E ECOG PERFORMANCE STATUS

APPENDIX F CASE REPORT FORMS

## **1.0 OBJECTIVES**

### **1.1 Primary Objective**

1.1.1. To evaluate the response rate of the combination of ablation and the PD-1 inhibitor nivolumab for patients with non-small cell lung cancer (NSCLC) who have progressed following at least 1 prior chemotherapy regimen for metastatic or locally advanced disease.

### **1.2 Secondary Objectives**

1.2.1 To evaluate the disease-free and overall survival for the combination of ablation and the PD-1 inhibitor nivolumab for patients with NSCLC who have progressed following at least 1 prior chemotherapy regimen for metastatic or locally advanced disease.

1.2.2 To evaluate whether ablation increases tumor PD-L1 expression.

## **2.0 BACKGROUND:**

**Lung Cancer:** Lung cancer is the most common cause of cancer death. Worldwide, in 2012 there were approximately 1.8 million new cases of lung cancer and an estimated 1.6 million deaths. In the United States, there will be an estimated 224,000 new cases of lung cancer and 159,000 deaths in 2014.

**Chemotherapy for Metastatic NSCLC:** First-line treatment for patients with advanced NSCLC without an EGFR or ALK mutation is combination chemotherapy generally including a platinum compound. Second-line chemotherapy often utilizes a single chemotherapy drug not utilized in the first-line regimen such as pemetrexed or docetaxel. Response rates to second line treatment are about 10%. The average survival for patients with metastatic NSLCC with multiple lines of chemotherapy is about 1 year.

**PD-1/PD-L1 Inhibition:** Stimulating the immune system to fight lung cancer represents one of the most remarkable clinical achievements in the last decade in thoracic oncology. Programmed death ligand 1 (PD-L1) is a transmembrane protein that was first identified for its role in the maintenance of self-tolerance and prevention of autoimmunity. Engagement of PD-L1 on dendritic cells with the programmed death 1 (PD-1) receptor on T cells delivers an inhibitory signal that promotes T cell anergy or apoptosis. This immunoinhibitory checkpoint is often subverted by tumor cells that over-express PD-L1 in order to escape immunosurveillance in the tumor microenvironment. There is a strong correlation between PD-L1 expression and prognosis in cancer. Blockade of the interaction between PD-L1 on tumor cells and PD-1 on T cells with anti PD-1/anti PD-L1 antibodies reverse T cell suppression within tumors, thereby promoting effective anti-tumor immune responses.

**Nivolumab in NSCLC:** Nivolumab is a fully human IgG4 PD-1 monoclonal antibody that binds to the PD-1 receptor and blocks its interaction with PD-L1 and PD-L2, thereby releasing PD-1 pathway-mediated inhibition of the immune response, including anti-tumor immune response.

Patients with advanced NSCLC who had been previously treated with a prior platinum-containing regimen received nivolumab at a dose of 1, 3, and 10 mg/kg. The maximum-tolerated dose was not reached in this trial, and all doses were found to be safe. In the initial phase expanded phase I study reported in the New England Journal of Medicine (NEJM) a total of 122 patients with NSCLC were enrolled. The majority of patients with NSCLC were heavily pretreated; 55% of patients received at least three prior lines of therapy. Results showed 15 percent of participants experienced a partial response, of whom 59 percent had response durations of six months or

longer. Disease response was seen in squamous as well as non-squamous histology (six of 18 patients [RR, 33%] with squamous histology and seven of 56 patients [RR, 12%] with non-squamous histology). Nivolumab has been well tolerated. Only 8% of the patients with NSCLC experienced grade 3 or 4 treatment-related AEs. The most common grade 3 and 4 treatment-related AEs in patients with NSCLC were fatigue, elevated AST, and pneumonitis. Nine patients (3%) of the total trial population developed pneumonitis.

Tumor PD-L1 expression appeared to be associated with response. Among the first 76 assessable patients with NSCLC without tumor expression of PD-L1 there were no documented tumor responses, but 36% of patients with tumor PD-L1 expression were objective responders in the NEJM article. However, the FDA granted approval of nivolumab in all patients with squamous cell NSCLC regardless of PD-L1 expression based on complete data of the entire 122 patients with NSCLC in the expanded phase I as well as subsequent BMS trials with nivolumab. Similarly, data with the Merck PD-1 antibody MK-3475, suggests that while activity in NSCLC is higher in tumors with PD-L1 expression, benefit appears to be present even in tumors without expression. In KEYNOTE-001 evaluating MK-3475, using the 50% cutoff point for PD-L1 expression, about 25% of patients with NSCLC were strongly positive for PD-L1 expression. The overall response rate to MK-3475 for both PD-L1–positive and –negative groups was 19%. Median progression-free survival was 14.1 weeks in the PD-L1–positive patients vs 9.3 weeks in the weakly positive (1%–49% cutoff) and negative patients. Overall survival was 9.3 vs 7.3 months, respectively, following MK-3475 in patients with NSCLC, which was not statistically significant between the groups.

Given the unprecedented response seen in heavily pretreated patients with NSCLC, the following phase III studies were initiated:

- Nivolumab Compared to Docetaxel in Previously Treated Metastatic Non-squamous NSCLC (CheckMate 057) NCT01673867.
- Nivolumab Compared to Docetaxel in Previously Treated Advanced or Metastatic Squamous Cell Non-small Cell Lung Cancer (NSCLC) (CheckMate 017) NCT01642004
- Nivolumab Versus Investigator's Choice Chemotherapy as First-Line Therapy for Stage IV or Recurrent PD-L1+ Non-Small Cell Lung Cancer (CheckMate 026) NCT02041533

On March 4th, 2015 Nivolumab received FDA approval to treat metastatic squamous cell lung cancer with progression on or after first-line chemotherapy based on results from Check Mate 057. Nivolumab's efficacy to treat squamous NSCLC was established in this randomized trial of 272 participants, of whom 135 received Nivolumab and 137 received docetaxel. The trial was designed to measure the effect on overall survival. Participants who received Nivolumab lived 3.2 months longer than those participants who received docetaxel.

At the annual meeting of the American Society of Clinical Oncology, May 30, 2015, the results of Checkmate 057 were released. A survival benefit of nivolumab as compared to docetaxel was demonstrated for patients with metastatic non-squamous cell lung cancer. The 12 month overall survival was 51% for nivolumab compared with 39% for docetaxel. The response rate was 19% for nivolumab versus 6% for docetaxel. Grade 3/4 toxicities were higher with docetaxel (20% versus 7%). Patients with tumors with PD-L1 expression had significant benefit with nivolumab as compared to docetaxel while tumors without PD-L1 expression had similar outcomes.

**Ablation as a Treatment For Cancer:** Ablation is a local modality that involves placing a needle or electrode under radiologic guidance into the center of a tumor and using heat or cold to

destroy a defined area. Dupuy et al has demonstrated that ablation is an important treatment for lung cancer. Radiofrequency ablation (RFA) emits a high frequency alternating current from the tip of an electrode into the tissue surrounding that electrode. As the ions within the tissue attempt to follow the change in the direction of the alternating current, their movement results in frictional heating of the tissue. As the temperature within the tissue becomes elevated beyond 60°C, cells begin to die, resulting in a region of necrosis surrounding the electrode. Ablation can be used both to kill tumor cells but also to relieve pain. Dupuy et al pioneered ablation to reduce pain from bone metastases and this currently is an FDA indication.

Cryoablation uses cold injury to kill tumors. This procedure uses liquefied gases such as argon that cool as they expand. This freezing process, unlike other ablative techniques, is unique in maintaining intact intracytoplasmic organelles and the cell ultrastructure, while opening up the plasma membrane to immune cell exposure thus inducing higher post-ablative immunogenicity. These intact tumor antigens are captured by dendritic cells and macrophages, thereby mounting a local and systemic immune response involving IL-1, IL-6 and nuclear factor- $\kappa$ B (NF- $\kappa$ B)-dependent cytokines such as TNF $\alpha$ . Histological studies have shown post-cryoablation tumor infiltrates of neutrophils, followed by substantial macrophage recruitment; ELISA studies have shown systemic elevation of tumor-specific antibodies, NK cell activity, increased tumor-specific T cell response in regional lymph nodes and the level of systemic circulating T cells. ***Therefore, since cryoablation enhances the immunogenicity of tumors, the combination of cryoablation and nivolumab may be synergistic.***

Recent data from Sloan Kettering suggests that thermal ablation may also activate the immune system. Serum interleukin-6 (IL-6) increases after thermal ablation. IL-6 is released by several cell types including type-2 helper T-cells (Th2), and plays a role in type-1 helper T-cells (Th1) and Th2 differentiation. Furthermore; heat-based ablation increases the proportions of circulating Th1 and CTLs more than cryoablation. Heat-based ablation therefore is another approach to enhance systemic anti-tumor immunity by increasing CTL levels and optimizing Th1/Th2 balance.

**Protocol Rationale:** Nivolumab releases the inhibition of the immune system against human cancers. Dramatic and sustained activity has been observed in advanced lung cancer. Ablation may stimulate the immune system by exposing new tumor antigens. Since tumors that express PD-L1 may be more likely to respond to nivolumab, if ablation increases PD-L1 expression (which has not been studied) this treatment may enhance the activity of nivolumab at both the treated site and in other, non-treated, tumors. Ablation is already an FDA approved treatment for cancer. Nivolumab was recently FDA approved for second line treatment of advanced squamous cell NSCLC. The goal of the study will be to determine if the combination of nivolumab and ablation has higher systemic activity than previously reported with nivolumab alone.

### **3.0 ELIGIBILITY:**

#### **3.1 Inclusion Criteria:**

3.1.1 Pathologically or cytologically confirmed NSCLC

3.1.2 Stage IIIB or stage IV.

3.1.3 Patient to meet either criterion A or B:

A) Patient must have progressed after at least 1 line of systemic treatment (IV or oral) for metastatic or locally advanced disease. Must provide documentation systemic treatment was for either locally advanced or metastatic. Must also provide scan or assessment to show most recent progression, pre-enrollment certifying progression of disease to meet inclusion eligibility of progression. Radiation does not count as 1 line.

FDA exemption 6/30/15, 6/30/15, 8/17/15 (for LOCR initial), Amendment #1 10/5/15 v 2 HS approval, Amendment # 2 11/9/15, Amendment #3 3/4/16, Amendment # 4 4/7/16, Amendment # 5 6/1/16 V2, Amendment # 6 7/7/16, Amendment # 7 11/16/16, Amendment # 8 2/22/17, Amendment #9 5/22/17

B) Patients progressing within 6 months of completion of neoadjuvant or adjuvant chemotherapy are also eligible without having treatment for metastatic disease (for example patient with stage I disease undergoes resection, receives systemic chemotherapy and then progresses to the liver (now stage IV) within 6 months of chemotherapy). Radiation does not count as 1 line.

3.1.4 Ablation for advanced lung cancer is being considered by the treating physician for treatment or prevention of symptoms such as pain, bleeding or obstruction- Documentation is required in writing by MD for this criterion.

3.1.5 At least 1 site of measurable disease that will not be treated with ablation. Sites to send confirmation on which lesion of measurable disease will not be ablated for tracking of response.

3.1.6 At least 3 weeks since prior systemic treatment and/or radiation therapy for patient's NSCLC (from treatment day 1 on study)

3.1.7. No brain metastases except for patients whose metastases have been removed by surgical resection or have had stereotactic radiation or gamma knife with no evidence of active disease on MRI within 28 days of starting treatment.

3.1.8. Eastern Cooperative Oncology Group (ECOG) Performance Status of 0-2.

3.1.9. Life expectancy of at least 12 weeks.

3.1.10. Required entry laboratory parameters within 14 days of study entry: Granulocytes  $\geq$  1000/ $\mu$ l; platelet count  $\geq$ 75,000/ $\mu$ l; Creatinine  $\leq$  1.5x upper limit normal mg/dl; Bilirubin  $<$  1.5x upper limit normal; AST  $\leq$  3 x upper limit of normal.

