#### **5.0 DOSE MODIFICATIONS OF NIVOLUMAB AND TOXICITY MANAGEMENT:**

Adverse events will be graded with the use of the National Cancer Institute Common Terminology Criteria for Adverse Events, version 4

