## **5.3 Hold treatment until recovery to grade 1 or resolution for:**

- 1) If AST or ALT >3 to 5 times ULN (grade 2) or total bilirubin >1.5 to 3 times ULN (grade 2): **Withhold treatment**; may resume therapy upon recovery to grade 0 or 1 toxicity (AST/ALT grade 1 is >ULN-3xULN, Total bilirubin grade 1 is >ULN-1.5xULN).

\*\*for possibly, probably or definitely related to nivolumab see section 5.3, 2.I below

\*\*AST or ALT >5 times ULN (grade 3) or total bilirubin >3 times ULN (grade 3) or severe/life-threatening immune-mediated hepatitis: **Permanently discontinue**. \*\*see section 5.3 (this section), 2\*\* below

- 2) Immune-mediated hepatitis:

- I. Grade 2 or higher transaminase elevations that are possibly, probably or definitely related to nivolumab (with or without total bilirubin elevations): Withhold treatment and initiate high-dose systemic corticosteroids (prednisone 1 to 2 mg/kg daily or equivalent)

\*\* Severe (grade 3) or life-threatening (grade 4) transaminase elevations: Permanently discontinue treatment and initiate high-dose systemic corticosteroids (prednisone 1 to 2 mg/kg daily or equivalent)

- 3) **Colitis:**

- I.** Grade 2 (duration >5 days): Also administer systemic corticosteroids (prednisone 0.5 to 1 mg/kg daily or equivalent) followed by a corticosteroid taper; may increase to prednisone 1 to 2 mg/kg daily (or equivalent) if colitis worsens or does not improve despite corticosteroid use
- II.** Grade 3: Also administer systemic corticosteroids (prednisone 1 to 2 mg/kg daily or equivalent) followed by a corticosteroid taper

- 4) **Pneumonitis:** Pneumonitis (grade 2); also administer high-dose systemic corticosteroids (prednisone 1 to 2 mg/kg daily or equivalent) followed by a corticosteroid taper

- 5) **Other immune-mediated toxicities:** Other immune-mediated toxicities; also administer high-dose systemic corticosteroids followed by a corticosteroid taper (over 1 month)

- 6) **Creatinine** >1.5 to 6 times ULN (grade 2 or 3) or >1.5 times baseline (grade 1): Withhold treatment; administer prednisone 0.5 to 1 mg/kg daily (or equivalent) followed by a corticosteroid taper; may resume therapy upon recovery to grade 0 or 1 toxicity. If toxicity worsens or does not improve, permanently discontinue and increase corticosteroid dose to prednisone 1 to 2 mg/kg daily (or equivalent).

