#### 5.4 Discontinue treatment (remove patient from study), for following:

- 1) AST or ALT >5 times ULN (grade 3) or total bilirubin >3 times ULN (grade 3) or severe/life-threatening immune-mediated hepatitis: **Permanently discontinue.**
- 2) Colitis
  - I. Colitis: (grade 4); also administer high-dose systemic corticosteroids (prednisone 1 to 2 mg/kg daily or equivalent) followed by a corticosteroid taper
  - II. Colitis (recurrent)
- 3) Pneumonitis  
Pneumonitis (grade 3 or 4); also administer high-dose systemic corticosteroids (prednisone 1 to 2 mg/kg daily or equivalent) followed by a corticosteroid taper
- 4) Inability to reduce corticosteroid dose to prednisone  $\leq$ 10 mg/day (or equivalent) within 12 weeks.
- 5) Other adverse reactions that are life-threatening, severe or grade 3 treatment related adverse reactions that recur, or persistent grade 3 treatment-related toxicity that does not recover to grade 1 or resolve within 12 weeks (except alopecia)..
- 6) Creatinine >6 times ULN (grade 4): Permanently discontinue; initiate high-dose systemic corticosteroids
- 7) Severe (grade 3) or life-threatening (grade 4) transaminase elevations: Permanently discontinue treatment and initiate high-dose systemic corticosteroids (prednisone 1 to 2 mg/kg daily or equivalent)

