## **11.0 ADVERSE DRUG REACTION (ADR) REPORTING**

***BrUOG considers the SAE reporting period to begin when the subject signs the study specific informed consent.***

This study will utilize the descriptions and grading scales found in the NCI Common Terminology Criteria for Adverse Events (CTCAE) version 4 for grading all adverse events. All appropriate treatment areas should have access to a copy of the CTCAE version 4. A copy of the CTCAE version 4 can be downloaded from the CTEP web site (<http://ctep.cancer.gov>).

An Adverse Event (AE) is defined as any untoward medical occurrence in a patient or clinical investigation subject administered a pharmaceutical product and that does not necessarily have to

FDA exemption 6/30/15, 6/30/15, 8/17/15 (for LOCR initial), Amendment #1 10/5/15 v 2 HS approval, Amendment # 2 11/9/15, 18  
Amendment #3 3/4/16, Amendment # 4 4/7/16, Amendment # 5 6/1/16 V2, Amendment # 6 7/7/16, Amendment # 7 11/16/16,  
Amendment # 8 2/22/17, Amendment #9 5/22/17

have a causal relationship with this treatment. An AE can therefore be any unfavorable and unintended sign (including an abnormal laboratory finding), symptom, or disease temporally associated with the use of Abraxane whether or not considered related to Abraxane. This includes any newly occurring event or previous condition that has increased in severity or frequency since the administration of drug.

During clinical trials, adverse events can be spontaneously reported or elicited during open-ended questioning, examination, or evaluation of a subject. (In order to prevent reporting bias, subjects should not be questioned regarding the specific occurrence of one or more adverse events.)

Adverse events (AEs) will be recorded in the case report form for the duration of the trial, regardless of whether or not the event(s) are considered related to trial medication. All AEs considered related to trial medication will be followed until resolution even if this occurs post-trial.

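### Entry criteria cap AST and bilirubin but not ALT, although ALT above 3x or 5x ULN holds or permanently stops nivolumab

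*Protocol*

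**What the plan says.** **Entry.** Protocol 3.1.10 ("Required entry laboratory parameters within 14 days of study entry") lists granulocytes, platelets, creatinine, bilirubin and AST. AST must be at or below 3x ULN and bilirubin below 1.5x ULN. ALT is not listed. The Appendix B checklist has bilirubin and AST lines and no ALT line. The only liver condition among the exclusions (3.2) is known hepatitis B or C. ALT is nevertheless measured: the section 6.0 calendar has it drawn pre-study within 14 days and before each cycle.

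**Hold.** Section 5.3 item 1 begins "If AST or ALT >3 to 5 times ULN (grade 2" and withholds treatment. Its restart rule is "may resume therapy upon recovery to grade 0 or 1 toxicity (AST/ALT grade 1 is >ULN-3xULN", so treatment resumes only at 3x ULN or less. A note adds "for possibly, probably or definitely related to nivolumab see section 5.3, 2.I below", which sends drug-related cases to the corticosteroid rule.

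**Discontinue.** Section 5.4 item 1 permanently stops treatment for "AST or ALT >5 times ULN (grade 3) or total bilirubin >3 times ULN (grade 3", and the heading of 5.4 removes the patient from study. Item 7 reads "Severe (grade 3) or life-threatening (grade 4) transaminase elevations: Permanently discontinue treatment and initiate high-dose systemic corticosteroids".

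**Hepatic section.** Section 5.5 has a pre-treatment part that classifies impairment by bilirubin and AST only, and an on-treatment part that repeats the AST-or-ALT thresholds.

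**The concern.** Entry limits and hold triggers should meet, so that nobody enters already inside the range that stops treatment. For AST and bilirubin they do. For ALT there is no entry limit to meet the trigger, so the stated rules admit a patient whose ALT is already in hold or discontinuation range.

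By the cycle 2 labs that patient would normally have had one nivolumab dose and the first ablation (4.2). Sites could then reasonably do different things with the same stable value: dose as usual, hold until ALT falls below where it started, or stop nivolumab for good. At stake are consistent handling and the meaning of a discontinuation for ALT, which might not reflect any on-study change. Baseline ALT is recorded, so attributing a later change would be harder but not impossible.

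**Working it through.** The plan gives no figure on this point to reproduce. The check sets the rules side by side and then does simple arithmetic on the thresholds.

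**1. Entry limit (3.1.10) against hold trigger (5.3), multiples of ULN**

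| Analyte | Entry limit | Hold trigger | Permanent stop (5.4) |
|---|---|---|---|
| AST | at or below 3 | above 3 | above 5 |
| Bilirubin | below 1.5 | above 1.5 | above 3 |
| ALT | none | above 3 | above 5 |

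Creatinine is only a partial parallel. Its entry limit of 1.5x ULN matches one trigger in 5.3 item 6, but a second trigger, above 1.5 times baseline, can fire below the entry limit.

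**2. An eligible patient.** Take ALT 6x ULN, AST 2x ULN, normal bilirubin and everything else in order. Nothing in 3.1.10, 3.2 or Appendix B excludes this patient. The pre-treatment part of 5.5 places the patient in its mild category, with no dose adjustment.

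**3. The same patient at cycle 2, ALT unchanged.**
- As worded, 5.4 item 1 and the on-treatment part of 5.5 require permanent discontinuation.
- With ALT at 4x instead, 5.3 item 1 requires a hold. Restart needs 3x or less, which is below the entry value of 4x.
- If section 5 is read through the adverse-event definition, an unchanged value is not a "newly occurring event or previous condition that has increased in severity or frequency since the administration of drug" and triggers nothing.

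Section 5 does not say which reading governs. Elsewhere it states such conditions when it wants them: 5.2 is restricted to drug-related toxicity, and creatinine in 5.3 item 6 has a baseline-relative trigger. Items 5.3(1) and 5.4(1) have neither for ALT.

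**4. Distance from entry to discontinuation.** For an entry ALT of x times ULN, reaching 5x takes a relative rise of 5/x − 1:

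| Entry ALT (x ULN) | Minimum rise to 5x |
|---|---|
| 3.0 | 66.7% |
| 3.5 | 42.9% |
| 4.0 | 25.0% |
| 4.5 | 11.1% |
| 4.9 | 2.0% |

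This matters even on the lenient reading. Moving from the 3x–5x band to above 5x goes from what 5.3 labels grade 2 to what 5.4 labels grade 3. That is an increase in severity, however small the rise.

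**5. Frequency.** The documents give none. For scale only, assume 0.1% to 1% of eligible patients have ALT above 5x with AST at or below 3x. Among 33 patients the expected number is 33 × 0.001 = 0.03 to 33 × 0.01 = 0.33. The chance of at least one is 1 − 0.999^33 = 3.2% to 1 − 0.99^33 = 28.2%. These results only restate the assumed inputs and are not evidence of how often this happens.

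**6. Design.** The Simon design's error rates depend on the stage sizes (18 and 33), the cut-offs (4 or fewer to stop, 11 or more to reject) and the response rates (20% and 40%). None of these involves ALT.

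**The case against.** The best defence is that the protocol separates baseline from on-treatment liver function on purpose. Both places that describe the liver before treatment, 3.1.10 and the first part of 5.5, use AST and bilirubin; ALT appears only with toxicity. Section 5 also opens with "Adverse events will be graded with the use of the National Cancer Institute Common Terminology Criteria for Adverse Events, version 4", which favours reading its rules as rules about adverse events. There are practical safeguards too: pre-study results go to the coordinating office before registration, 5.1 lets the investigator delay a dose for a laboratory abnormality, and section 12.0 lets the physician stop treatment.

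Much of this stands, and it rules out some stronger readings that a reader might infer:

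- **That the patient must be held or discontinued before the first dose**, because the study calendar (footnote F) lets screening labs serve for cycle 1. This is the least natural reading. Section 5 speaks of withholding, resuming and discontinuing, which presuppose treatment already begun, and 5.5 keeps the two periods apart.
- **That high-dose steroids are mandatory for a pre-existing elevation.** Only the standalone wording of 5.4 item 7 suggests it. In 5.3 item 2 and in 5.5 the same instruction sits under immune-mediated hepatitis, and 5.3 item 1 points to a rule based on attribution to nivolumab.
- **That the trial's error rates suffer.** Nothing in the documents supports that.

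The defence does not settle cycle 2. Those labs are on-treatment on any reading, and neither 5.3(1) nor 5.4(1) makes an exception for a value present at entry. The safeguards are case-by-case judgement and give the registering office no ALT criterion to apply.

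**Conclusion.** The point holds as a minor safety and internal-consistency gap. That ALT has no entry limit, while ALT alone can hold or end treatment, is certain from the text. What happens to an eligible patient with a raised, stable ALT depends on how section 5 is read: as worded, a hold or permanent discontinuation at cycle 2; if confined to new or worsened events, nothing until ALT worsens. The protocol does not choose between these. In size, entry ALT has no ceiling against triggers at 3x and 5x ULN, and the rise that separates entry from discontinuation can shrink from about 67% to nearly nothing. An ALT this high with AST at or below 3x ULN is probably rare, but that is a judgement the documents cannot confirm.

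**What to change.** Add an ALT limit of 3x ULN or less to 3.1.10 and one matching line to the Appendix B checklist, as already exists for AST. No new test is needed, because ALT is already drawn at screening. The cost is one term, one checklist line and a very small loss of eligible patients. Sample size and decision rule stay as they are.

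This aligns ALT with AST and removes most of the conflict, but not all of it. Entry labs may be up to 14 days old, so ALT can still pass 3x between screening and the first dose. A sentence in section 5 on elevations already present before dosing would cover that remainder, if the sponsor wants it closed.
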